6.4.2. Handling of Dropouts and Missing Data

To minimize missing data due to early treatment discontinuation and toxicity, patients are strongly encouraged to complete all visits until they withdraw from the study under the treatment

Statistical Analysis Plan for Protocol ABSK-021-301

policy strategy. The following analyses will be conducted to assess the timings, patterns, and reasons for missing data from the study.

Tabular summaries will be presented to show the percentage of patients who discontinue their randomized treatment or withdraw from the study by treatment group. Kaplan-Meier plots will be used to present the time from the first dose to discontinuation of randomized treatment or withdrawal from the study, with further analysis split by treatment-related or non-treatment-related reasons for discontinuation. If necessary, additional exploratory analyses will be conducted to better understand the pattern of missing data based on these outputs.

For ORR-TVS, the same approach described for the primary efficacy ORR will be employed.

The primary analysis of the key secondary endpoints (excluding ORR-TVS) will use mixed models for repeated measurements (MMRM) that incorporate all available measurements from each patient under the missing completely at random (MCAR) and the missing at random (MAR) assumptions.

For sensitivity analysis of longitudinal continuous endpoints, including relative ROM, Worst-Stiffness-NRS, Worst-Pain-NRS, and PROMIS-PF T-scores, under missing not at random (MNAR), the control-based pattern mixture models (PMM), specifically, Jump to Reference (J2R), Copy Reference (CR) and the tipping point analysis (a type of PMM with delta adjustment) (Sande V. et. al. 2021⁹) will be performed. Details will be described in [Section 6.4.4](#) below.

6.4.3. Primary Analysis of Key Secondary Endpoints

6.4.3.1. BIRC-25-Week ORR based on TVS

The BIRC-25-Week ORR based on TVS will be based on the ITT analysis set and primarily analyzed using the same method as the primary endpoint. The treatment effect on the ORR will be formally tested at the 2-sided significance level of 0.05 using Fisher's exact test only if the statistically significant treatment effect on the 25-Week ORR by BIRC has been established. Otherwise, p-value will be presented for the purpose of demonstrating trends.

The number and percentage of patients in each category of Best Overall Response (BOR) by the BIRC based on TVS (CR, PR, SD, PD, or NE) will be presented by treatment group. A similar summary of the ORR for each treatment group along with their exact two-sided 95% CIs using the Clopper-Pearson method will be provided.

6.4.3.2. Relative ROM at Week 25

The primary analysis of change from baseline in relative ROM at Week 25 will be conducted based on the ITT analysis set. A mixed model for repeated measures (MMRM) will be employed with use of all available data from baseline up to Week 25 visit. The MMRM model will include change from baseline as the dependent variable, and treatment, baseline, visit, stratification-factor of China vs. non-China sites, and treatment-by-visit interaction, baseline-by-visit interaction, joint-type-category (knee, ankle and others) as fixed effects. For the model, the restricted maximum likelihood (REML) estimation will be used along with Kenward-Roger

Statistical Analysis Plan for Protocol ABSK-021-301

approximation for estimation of the degrees of freedom. To account for the variability in measurements within patients, an unstructured variance-covariance matrix will be used. If the fit of the unstructured covariance structure fails to converge, compound symmetry will be employed. The least squares mean (LSMEAN) for each treatment, and the treatment difference (ABSK021 – Placebo) in LSMEAN along with its' 95% CI and p-value will be provided for scheduled visits at Week 13 and Week 25. A formal statistical comparison between treatment groups will only be made at Week 25 following the prespecified order in the hierarchical gatekeeping testing procedure. In addition, a line plot showing LSMEAN of change from baseline along with standard error (SE) bars over time in Part 1 will be produced by treatment group.

The derived relative ROM and the change from baselines at each scheduled visit will be summarized descriptively by the treatment group. A line plot showing observed mean along with standard error bars over time will be produced by treatment group.

In addition, a table will be prepared to summarize the distribution of the mean scores used for analysis.

6.4.3.3. Worst-Stiffness-NRS at Week 25

The change from baseline in Worst-Stiffness-NRS at Week 25 will be analyzed based on the ITT analysis set using a mixed model for repeated measures (MMRM) with use of all data from baseline up to Week 25 visit. The model will include change from baseline as the dependent variable, and treatment, baseline, visit, stratification-factor of China sites vs. non-China sites, and treatment-by-visit interaction and baseline-by-visit interaction as fixed effects. For the model, the restricted maximum likelihood (REML) estimation will be used; an unstructured variance-covariance matrix will be used to model the within-patient error and the Kenward-Roger approximation will be used to estimate the degrees of freedom. If the fit of the unstructured covariance structure fails to converge, the following covariance structures will be tried in order until convergence is reached: toeplitz with heterogeneity, autoregressive with heterogeneity, toeplitz, autoregressive and compound symmetry. The least squares mean (LSMEAN) for each treatment, and treatment difference (ABSK021 – Placebo) in LSMEAN along with its' 95% CI and p-value will be provided for each scheduled visit. A formal statistical comparison between treatment groups will only be made at Week 25 following the prespecified order in the hierarchical gatekeeping testing procedure. In addition, a line plot showing LSMEAN of change from baseline along with standard error (SE) bars over time in Part 1 will be produced by treatment group.

Descriptive statistics will be used to summarize the Worst-Stiffness-NRS and the change from baselines at each scheduled visit by treatment group. A line plot showing observed mean along with SE bars over time will be produced by treatment group.

In addition, a table will be prepared to summarize the distribution of the mean scores used for analysis.

6.4.3.4. BPI-Worst-Pain-NRS at Week 25

The change from baseline in BPI-Worst-Pain-NRS will be primarily analyzed by employing the same method described for the Worst-Stiffness-NRS. A formal statistical comparison between treatment groups will only be made at Week 25 following the prespecified order in the hierarchical gatekeeping testing procedure. In addition, a line plot showing LSMEAN of change from baseline along with standard error (SE) bars over time in Part 1 will be produced by treatment group.

Descriptive statistics will be used to summarize the BPI-Worst-Pain-NRS and the change from baselines by treatment group at each scheduled visit. A line plot showing observed mean along with SE bars over time will be produced by treatment group.

In addition, a table will be prepared to summarize the distribution of the mean scores used for analysis.

6.4.3.5. PROMIS PF T-score at Week 25

The change from baseline in PROMIS PF T-score will be primarily analyzed by employing the same method described for the Worst-Stiffness-NRS. All valid T-scores from the Service platform will be included in the model. Any non-valid score will be set to missing. For a T-score to be considered valid, a minimum of 4 non-missing items are utilized for deriving the score. A formal statistical comparison between treatment groups will only be made at Week 25 following the prespecified order in the hierarchical gatekeeping testing procedure. In addition, a line plot showing LSMEAN of change from baseline along with standard error (SE) bars over time in Part 1 will be produced by treatment group.

Descriptive statistics will be used to summarize the PROMIS PF T-score and the change from baselines by treatment group at each scheduled visit. A line plot showing observed mean along with SE bars over time will be produced by treatment group.

In addition, a table will be prepared to summarize the distribution of the T-score.

6.4.4. Sensitivity Analysis of Key Secondary Endpoints**6.4.4.1. Sensitivity Analyses of BIRC-25-Week ORR based on TVS**

Sensitivity Analyses of BIRC-25-Week ORR based on TVS will follow the same approach described for the primary efficacy ORR in [Section 6.3.4](#).

6.4.4.2. Sensitivity Analyses of Continuous Key Secondary Endpoints

Sensitivity analyses will be performed to examine the robustness of the results obtained from the primary analysis of continuous key primary endpoints under the treatment policy estimand using missing not at random (MNAR) assumption. These sensitivity analyses will consider possible departures from the underlying assumptions, specifically under MNAR scenarios. The following control-based pattern mixture models (PMM) will be used.

Jump to Reference (J2R):

In this sensitivity analysis, intermittent missing values (i.e., Week 13 value is missing while Week 25 value is available) will be imputed using the Markov Chain Monte Carlo (MCMC) methodology, which assumes a multivariate normal distribution over all variables included in the imputation model. This imputation will be done by treatment group, using the MI procedure in SAS 9.4. The variables to be used in the imputation are treatment, corresponding baseline values, and values observed at all double-blind visits (Week 13 and Week 25). Then all the monotone missing values will be multiply-imputed using the imputation model built from the Placebo group, but only from the point of missing time point (i.e., jump to reference). Once the completed data sets are formed, the same MMRM analysis model for the primary analysis as specified in [sections 6.4.3.2](#), [6.4.3.3](#), [6.4.3.4](#), [6.4.3.5](#) will be applied to each completed set, and the inference will be drawn using Rubin's combination rules (SAS proc MIANALYZE).

Copy Reference:

In this sensitivity analysis, like the J2R imputation method, intermittent missing values will be imputed using the Markov Chain Monte Carlo (MCMC) methodology. Then all the monotone missing values will be multiply-imputed using the imputation model built from the Placebo group, i.e., assuming the missing data in the ABSK021 treatment group will have a profile that equals the profile of the Placebo group for all time points (i.e., a copy-reference imputation). Once the completed data sets are formed, the same MMRM analysis model for the primary analysis as specified in [sections 6.4.3.2](#), [6.4.3.3](#), [6.4.3.4](#), [6.4.3.5](#) will be applied to each completed set, and the inference will be drawn using Rubin's combination rules (SAS proc MIANALYZE).

Tipping point:

In this sensitivity analysis, like the above imputation methods, intermittent missing values will be imputed using the Markov Chain Monte Carlo (MCMC) methodology. Then for the ABSK021 treatment group, add a range of constant delta (penalties) directly onto the imputed values, specifically reductions for ROM and PROMIS-PF T-score and increases for stiffness and pain scores, to worsen the treatment effect. It is desired to impose a fixed and definite set of quantities to encapsulate the change in efficacy associated with missing for the ABSK021 treatment group while missing for the Placebo treatment group is following the MAR assumption.

The analysis finds a tipping point in this spectrum of assumptions of delta, at which statistically significant conclusions change from being favorable ($p < 0.05$) to the ABSK021 treatment to being unfavorable ($p > 0.05$).

Patient Disposition and Summary of Missing Data for PROs

Table summarizing PRO data completeness will be provided. The denominator used to evaluate data completeness differs based on the PRO objective. When the PRO objective is clinical benefit (i.e., ROM, Worst-Stiffness, BPI-Worst-Pain, and PROMIS-PF), the percentage for available data rate and each missing category will be calculated using the randomized population as the fixed denominator.

Within the tables, counts and percentages of patients who completed and did not complete the PRO measure will be calculated with the accompanying reasons for missing observations (including intercurrent event categories) based on collected data.

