6.4.1.3. Worst Stiffness Numeric Rating Scale (NRS)

Speck R. et al. (2019 [7](#)) described the content validity of the measures of these 2 PROs for patients with tenosynovial giant cell tumors (TGCT). Worst Stiffness NRS and PROMIS-PF have good reliability, validity, and responsiveness, and provide guidance for the interpretation of meaningful change in TGCT patients (Speck R. et al. 2020⁸). The Worst-Stiffness-NRS item is a one-item self-administered questionnaire assessing the “worst” stiffness in the last 24 hours. The NRS for this item ranges from 0 (“no stiffness”) to 10 (“stiffness as bad as you can imagine”). The instrument will be measured at Screening, Week1, Week 5, Week 9, Week 13, Week 17, Week 21 and Week 25 visits during Study Part 1. Except for Week 1 (C1D1), patients are required to complete the Worst-Stiffness-NRS assessments for at least 4 of 7 consecutive days during each scheduled visit. The assessment at Week 1 (C1D1) should be completed prior to the first dosing. Consequently, a minimum of 4 out of the consecutive 7 days will be required to compute the mean of NRS score for each post-dose visit; otherwise, it will be set to missing. The baseline will be derived based on the mean score of evaluations completed prior to randomization, specifically, at least 4 of 7 consecutive days during the 2 weeks prior to randomization, and on C1D1. If there are multiple consecutive 7-day assessments, the baseline will be calculated using the most recent 7-day assessments, in addition to C1D1.

The change from baseline will be calculated for each scheduled visit by subtracting the mean baseline value from each post-baseline mean value. If either the baseline value or the post-baseline value is missing, the change will be set as missing.

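### The MNAR imputation step in SAP 6.4.4.2 names only Weeks 13 and 25, which fits range of motion but not the three patient-reported endpoints measured at six post-baseline visits

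*SAP*

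**What the plan says.** SAP 6.4.2 puts four continuous endpoints in scope for the MNAR analyses, "including relative ROM, Worst-Stiffness-NRS, Worst-Pain-NRS, and PROMIS-PF T-scores, under missing not at random (MNAR"). SAP 6.4.4.2 then gives the mechanics, mostly in the J2R paragraph:

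- The first step fills "intermittent missing values (i.e., Week 13 value is missing while Week 25 value is available") by MCMC within treatment group.
- The variables in that model are treatment, the corresponding baseline and "values observed at all double-blind visits (Week 13 and Week 25").
- Remaining monotone gaps are imputed from a model built on the placebo group.
- Each completed data set goes to "the same MMRM analysis model for the primary analysis as specified in" SAP 6.4.3.2 to 6.4.3.5, which covers ROM and all three PROs.

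Copy reference and tipping point give no visit list of their own. Copy reference says "like the J2R imputation method, intermittent missing values will be imputed using the Markov Chain Monte Carlo (MCMC) methodology". Tipping point says "like the above imputation methods, intermittent missing values will be imputed using the Markov Chain Monte Carlo (MCMC) methodology".

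The schedules differ by endpoint. SAP 6.4.1.2 measures ROM after baseline at Weeks 13 and 25. SAP 6.4.1.3 measures stiffness at Screening and "Week1, Week 5, Week 9, Week 13, Week 17, Week 21 and Week 25 visits during Study Part 1", and SAP 6.4.1.4 and 6.4.1.5 give the same weeks for pain and PROMIS-PF. Week 1 is completed before the first dose and forms part of baseline. SAP Table 4.2 and protocol Table 1 agree. Protocol 7.4.4.2 names the three methods but lists no visits.

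**The concern.** The visit list and the definition of intermittent missingness match one of the four endpoints that the section governs. For the other three the written rule cannot be followed as it stands, and the SAP has no separate imputation specification for the PROs.

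These are the only MNAR analyses planned for key secondary endpoints 3 to 5. The supportive analysis in SAP 6.4.5 changes the handling of alternative anti-tumor therapy and does not test the missing-data assumption. If the rule is open to more than one reading, two programmers could produce different J2R, copy-reference and tipping-point results from the same data, and the choice could be made after unblinding.

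A smaller point concerns covariates. The stated imputation variables omit region, which is in every MMRM. They also omit joint type, which SAP 6.4.3.2 includes for ROM ("joint-type-category (knee, ankle and others) as fixed effects").

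**Working it through.** **1. Visits and missingness patterns.** With k post-baseline visits there are 2^k patterns, of which k + 1 are monotone and 2^k − k − 1 are intermittent.

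| Endpoint | Post-baseline visits | k | Patterns | Monotone | Intermittent |
|---|---|---|---|---|---|
| Relative ROM | Weeks 13, 25 | 2 | 4 | 3 | 1 |
| Stiffness, pain, PROMIS-PF | Weeks 5, 9, 13, 17, 21, 25 | 6 | 64 | 7 | 57 |

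The SAP wording defines the single intermittent pattern that exists for ROM. For the PROs it leaves out four of six visits (Weeks 5, 9, 17 and 21), and nothing says how gaps at those visits are filled.

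**2. The literal rule applied to PRO patients.**

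- Seen at every visit to Week 21, missing Week 25: imputed from baseline and Week 13. Weeks 17 and 21 are not used.
- Missing Weeks 13 and 25, seen at Weeks 17 and 21: on two visits this looks like dropout after baseline, so Week 13 is imputed from the placebo model although the patient was seen later. On six visits the Week 13 gap is intermittent.
- Seen at Week 13, last seen at Week 17 or 21: J2R switches to the reference from the visit at which data go missing. With only Weeks 13 and 25 in the model, that point is undefined between them.
- Any patient missing Week 5, 9, 17 or 21: the data set is not completed at that visit, yet it is passed to a six-visit MMRM as a completed set.

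**3. Size for one imputed value.** The documents give no correlations, so these are assumptions. For a patient last seen at Week 21, the residual variance of Week 25 as a share of its total variance is 1 − r′R⁻¹r. Here R is the correlation matrix of the predictors and r their correlations with Week 25. Visits are equally spaced at four weeks.

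*AR(1), adjacent-visit correlation 0.8.* Only the latest observed visit matters, so baseline adds nothing.
- Literal rule (Week 13, three steps back): 1 − (0.8³)² = 1 − 0.262 = 0.738.
- All visits to Week 21 (one step back): 1 − 0.8² = 0.360.
- Ratio: 0.738 / 0.360 = 2.05.

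*Compound symmetry, correlation 0.6.* With m predictors the residual is 1 − m × 0.36 / (1 + (m − 1) × 0.6).
- Literal rule (baseline and Week 13, m = 2): 1 − 0.72 / 1.6 = 0.55.
- Baseline and Weeks 5 to 21 (m = 6): 1 − 2.16 / 4.0 = 0.46.
- Ratio: 0.55 / 0.46 = 1.20.

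Results over a range of assumed correlations, with baseline included throughout:

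| Correlation | CS, literal | CS, all visits | Ratio | AR(1), literal | AR(1), all visits | Ratio |
|---|---|---|---|---|---|---|
| 0.5 | 0.667 | 0.571 | 1.17 | 0.984 | 0.750 | 1.31 |
| 0.7 | 0.424 | 0.347 | 1.22 | 0.882 | 0.510 | 1.73 |
| 0.8 | 0.289 | 0.232 | 1.25 | 0.738 | 0.360 | 2.05 |
| 0.9 | 0.147 | 0.116 | 1.27 | 0.469 | 0.190 | 2.47 |

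The loss is modest if all visits are equally correlated and larger if correlation decays with time.

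**The case against.** The strongest reply is that the bracket was carried over from ROM and the intent is plain. The general phrase in front of it refers to every double-blind visit, and the same paragraph requires completed data sets for the MMRM of SAP 6.4.3.3, which uses all data up to Week 25. Two-visit imputation cannot complete a six-visit data set, so the section itself points to all six visits. This stands as evidence of intent. It is why the defect is best described as a wrong visit list that also contradicts its own context, rather than a decision to discard data. It does not remove the need for correction, because both the bracket and the definition of intermittent missingness state Weeks 13 and 25 explicitly.

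A second reply is that the effect on the estimate is small. Under MAR, suppose 15% of an arm is missing Week 25 (borrowing the dropout figure in SAP 1.3) and all were last seen at Week 21. The variance of the arm mean is then proportional to R² + (1 − R²)/0.85. Under AR(1) 0.8 this is 0.262 + 0.738/0.85 = 1.130 for the literal rule, against 0.640 + 0.360/0.85 = 1.064 with all visits. The standard error rises by the square root of 1.130/1.064, about 3%. PRO collection after discontinuation is also encouraged, which should limit missingness. This is fair for precision, but it does not cover misclassified patterns or the undefined jump point.

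Two stronger readings are tempting and not supported. A reader might infer that copy reference starts from the wrong visit. It has no starting visit: the SAP gives the missing data the placebo profile at all time points. A reader might also infer that the tipping point would be misplaced. Nothing in the documents allows the direction or size of a shift to be derived.

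The covariate omission is real but secondary. Region is a randomization stratum and should be roughly balanced, and no bias in the treatment contrast is shown.

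**Conclusion.** The point holds as a specification error of limited reach. For Worst Stiffness, Worst Pain and PROMIS-PF, the imputation visits and the intermittent pattern in SAP 6.4.4.2 are wrong on their face and inconsistent with the MMRM that the section then calls for. For ROM they are correct.

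The visit counts and pattern counts come directly from the SAP. The variance ratios of about 1.2 (compound symmetry 0.6) and 2.05 (AR(1) 0.8) rest on assumed correlations and describe one imputed value for a patient last seen at Week 21. They do not measure the effect on the treatment difference.

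Only the MNAR sensitivity analyses of key secondary endpoints 3 to 5 are affected. The primary ORR test, the primary MMRMs and the gatekeeping sequence are untouched, so an inference that the formal conclusions are at risk would go too far. The correction should still be made, because these analyses are the only planned check on the missing-at-random assumption for those endpoints.

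**What to change.** In SAP 6.4.4.2:

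1. List the imputation visits by endpoint: relative ROM, Weeks 13 and 25; Worst Stiffness, Worst Pain and PROMIS-PF, Weeks 5, 9, 13, 17, 21 and 25.
2. Define intermittent missing as any missing visit followed by a later observed visit, and monotone missing as all visits missing from a given visit onward. Apply both on the endpoint's own visit list.
3. State that these definitions hold for J2R, copy reference and tipping point alike.

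As a secondary suggestion, add region, and joint type for ROM, so that the imputation model contains the MMRM covariates, where the small placebo arm allows. The first step runs by arm with about 30 placebo patients. Baseline plus six visits already means 7 means and 7 × 8 / 2 = 28 variances and covariances, so a fallback for non-convergence should be named.

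The cost is a few lines of SAP text and minor programming. It should be done before the Part 1 database lock, the point by which SAP section 1 says the plan will be final. No data collection or sample size changes.

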6.4.5. Supportive Analyses of Key Secondary Endpoints

ROM and PROs under Different Strategy to the Intercurrent Event

For intercurrent event of receiving an alternative anti-tumor therapy (including surgery), while on treatment policy will be used for ROM and PROs as the sensitivity analyses. The similar MMRM model as the primary analysis of ROM and PROs will be used. The data after receiving an alternative anti-tumor therapy (including surgery) will not be included in the analyses.

BPI-30

A BPI-30 responder will be defined as a patient who (i) experienced a decrease of at least 30% in the mean BPI Worst Pain NRS item AND (ii) did not experience a 30% or greater increase in narcotic analgesic use, comparing data collected in concomitant medication during a 7-day period at the end of Part 1 compared with baseline values collected prior to the first dose of study treatment. Patients who do not provide data for the endpoint will be considered to be non-responders. Analgesic use will also be recorded in BPI visit and linked to concomitant medication page. If a patient didn't use analgesic medication at baseline but used it at post-baseline, it's regarded as a 30% or greater increase in narcotic analgesic use. If a patient used the same analgesic medication at baseline and post-baseline, the change in analgesic use should be calculated by the change in patients' mean analgesic use that calculated by multiplying the daily dose unit by the number of units taken, averaged by the number of days with available data in concomitant medication. If a patient used different analgesic medications at baseline and post-baseline, whether a 30% or greater increase in analgesic use will be judged by medical review case by case.

The BPI-30 responders will be summarized by treatment group based on ITT. The treatment comparison of BPI-30 will be based on Fisher's exact test.

Responder Summary of COAs (i.e., ROM and PRO) by Clinical Thresholds

Descriptive by-treatment responder summary of the COAs change from baseline at Week 25 by thresholds of clinically meaningful within-patient change will be performed, such as 5%, 6.7%, 10%, 15%, 20%, and 25% for ROM; 1 point improvement for Worst Stiffness and 3 points improvement for PROMIS-PF T-scores (Speck et al., 2020⁸), and 1 point improvement for BPI (Dworkin et al., 2008¹⁰).

Statistical Analysis Plan for Protocol ABSK-021-301

eCDF and ePDF Plots

Empirical cumulative distribution function (eCDF) and empirical probability density function (ePDF) of COAs (ROM, Worst Stiffness, BPI and PROMIS) changes from baseline at Week 25 for each treatment group will be prepared.

Correlation Analyses for Key Secondary Endpoints

To investigate the correlation between the treatment effect on tumor responses and improvements in key secondary clinical outcome assessments (COA), including change from baseline to Week 25 in relative ROM, Worst-Stiffness-NRS, Worst-Pain-NRS, and PROMIS-PF T-scores (named change below), the following descriptive summaries and subgroup analyses will be carried out at Week 25. For the tumor response assessment, BIRC evaluations based on the RECIST v1.1 criteria will be used, unless specified otherwise.

- A scatter plot of percent change in tumor size at X-axis and change in each COA at Y-axis with fitting in a nonparametric local regression (Loess) line and 95% CI will be provided, respectively.
- Spearman's rank-order correlation coefficients will be provided between the percentage change in tumor size and change for each COA, respectively.
- A waterfall plot of the change by tumor responder status by treatment group for each COA, respectively.
- Responder subgroup analysis of the change by tumor responder status will be performed. The evaluation will use a similar approach for the primary analysis of each COA endpoint, with the addition of three fixed factors (subgroup, subgroup-treatment interaction, subgroup-treatment-visit interaction) into the corresponding MMRM model.

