5.9 Concomitant therapy

5.9.1 Permitted Medications

In general, in addition to prohibited medications and treatments specified in the protocol, the Investigator may provide supportive care for disease-related symptoms as clinically indicated, and care should be performed according to the site standard of care procedures. Patients may also receive medication for symptom relief (e.g., antidiarrheals, antiemetics, etc.).

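### SAP 6.4.5 defines BPI-30 on narcotic analgesic use, but its derivation counts any analgesic started after an analgesic-free baseline as a narcotic increase

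*SAP*

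**What the plan says.** SAP 6.4.5 (BPI-30) sets two conditions for a responder. Condition (i) is that the patient "experienced a decrease of at least 30% in the mean BPI Worst Pain NRS item". Condition (ii), on medication, is that the patient "did not experience a 30% or greater increase in narcotic analgesic use". Analgesic data from the concomitant-medication record are compared "during a 7-day period at the end of Part 1 compared with baseline values collected prior to the first dose of study treatment". A patient without endpoint data is classed as a non-responder.

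Three derivation rules follow.

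- **Rule 1, no analgesic at baseline but some afterwards:** the patient is "regarded as a 30% or greater increase in narcotic analgesic use".
- **Rule 2, same analgesic at both times:** the rule opens "If a patient used the same analgesic medication at baseline and post-baseline, the change in analgesic use should be calculated by the change"; the quantity that changes is mean use, taken as daily dose unit times number of units, "averaged by the number of days with available data in concomitant medication".
- **Rule 3, different analgesics at the two times:** whether use rose by 30% or more "will be judged by medical review case by case".

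BPI-30 is summarised on the ITT set and compared between arms with Fisher's exact test. It is not one of the five key secondary endpoints in SAP 6.2, which says that analyses outside the hierarchy receive no multiplicity adjustment and that their p-values are nominal. The protocol does not define BPI-30.

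**The concern.** The criterion concerns narcotics. Rule 1 is triggered by analgesic medication of any class, and rules 2 and 3 speak only of analgesic use. A programmer therefore has two different endpoints to choose between, and rule 1 read literally gives a result that the criterion does not.

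The rule can have patients to act on. Protocol 4.2.1 asks for a stable analgesic regimen only from patients with an analgesic need (criterion 5) and admits patients on stiffness alone (criterion 7), so analgesic-free baselines are possible. Protocol 6.4.10 collects analgesics by name and dosage with no limit on class. Under Protocol 5.9.1, "the Investigator may provide supportive care for disease-related symptoms as clinically indicated", so new symptomatic medication during Part 1 is also possible.

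What is at stake is the one planned efficacy analysis that takes analgesic use into account. The pain estimand in SAP 1.1 keeps NRS data after a change in background analgesics. The alternative-strategy analysis in SAP 6.4.5 deals only with alternative anti-tumor therapy.

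**Working it through.** The documents give no expected rate, power or event count for BPI-30, so there is no stated figure to reproduce. The check applies the rules to example patients.

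**Step 1: criterion against rule 1.** Take a patient whose mean worst pain falls by 80%, who used no analgesic at baseline and who takes one non-narcotic dose in the final 7-day period.

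- Criterion (i): 80% ≥ 30%, met.
- Criterion (ii) as stated: narcotic use is 0 before and 0 after, so there is no increase. The patient is a responder.
- Rule 1 as stated: no baseline analgesic and some later analgesic, so a narcotic increase is deemed. The patient is a non-responder.

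The two statements in the same paragraph give opposite answers, and no assumption about the data is needed to see it. Rule 1 covers only patients with no analgesic at baseline. A switch goes to rule 3. An analgesic added to a continuing one is not clearly covered by any rule.

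**Step 2: the denominator in rule 2.** Compare two readings of days with available data:

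- recorded-use days only: mean = total units ÷ number of days with intake;
- full window: mean = total units ÷ 7, with known no-intake days as zero.

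| Baseline week | Final week | Change, recorded-use days | Change, 7 days |
|---|---|---|---|
| 1 unit on 1 day | 1 unit on 7 days | 1/1 to 7/7: 0% | 1/7 to 7/7: +600% |
| 1 unit on 5 days | 1 unit on 7 days | 5/5 to 7/7: 0% | 5/7 to 7/7: +40% |
| 1 unit on 7 days | 2 units on 2 days | 7/7 to 4/2: +100% | 7/7 to 4/7: −43% |
| 1 unit on 7 days | 2 units on 3 days | 7/7 to 6/3: +100% | 7/7 to 6/7: −14% |

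Against the 30% limit, the first two rows pass on recorded-use days and fail over seven days. The last two do the reverse. If no-intake days already count as available data with value zero, and no day is missing, both denominators are 7 and rule 2 causes no error. The SAP does not say which reading applies. It also gives no length for the baseline analgesic window; seven days is assumed in the table.

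**Step 3: size.** With the planned 60 and 30 patients, one reclassified patient moves the ABSK021 rate by 1/60 = 1.7 points or the placebo rate by 1/30 = 3.3 points. For a range, assume (the documents give no rates) that 60% on ABSK021 and 30% on placebo meet criterion (i), a difference of 30 points, and that rule 1 removes a share of them:

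- 10% in both arms: 0.60 × 0.90 − 0.30 × 0.90 = 0.54 − 0.27 = 27 points;
- 10% on ABSK021, 30% on placebo: 0.54 − 0.30 × 0.70 = 0.54 − 0.21 = 33 points;
- 20% on ABSK021, 5% on placebo: 0.60 × 0.80 − 0.30 × 0.95 = 0.48 − 0.285 = 19.5 points.

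These figures show what rule 1 could do under assumed shares. They do not estimate what it will do.

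**The case against.** Four things can fairly be said for the plan.

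**Rule 1 may be shorthand, or deliberately conservative.** It ends by referring to narcotic use, so analgesic medication may simply mean the narcotics named in criterion (ii). Read literally, it refuses to credit a pain fall that coincides with new analgesia, which is a defensible design. Either intention is reasonable, but the text states neither, and the literal rule contradicts the literal criterion. The inconsistency stands.

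**The denominator is not shown to be wrong.** A reader might infer that concomitant-medication records exist only for days of use, and so that rule 2 hides rises in frequency. The documents do not say so. SAP 6.4.5 adds that analgesic use is also recorded at the BPI visit and linked to the medication page, so a day of known zero intake may well be a day with data. This objection stands: the +600% case is conditional on one reading of an undefined term.

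**No unblinded review is planned.** A reader might infer that drug switches will be judged with treatment known. Protocol 5.7.1 and SAP 1.4 keep the sponsor and sites blinded in Part 1, and Protocol 7.3.1 requires data to be cleaned before codes are unblinded. What remains is narrower. SAP 3.3 places the assessment of major deviations in a blinded review meeting before lock, while the BPI-30 review has no stated timing or criteria.

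**The consequence is small.** BPI-30 is supportive, and treatment policy for analgesic changes is an explicit estimand choice. SAP 5.5.3 tabulates concomitant medication by class and name for each arm, so a marked imbalance in analgesic use would be visible. This also stands. A reader might go further and conclude that the between-arm comparison is wrong. That does not follow, because the rules are the same in both arms and no document gives the number of affected patients.

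**Conclusion.** The point holds for rule 1. A stated derivation rule conflicts with the stated criterion and, followed literally, makes a patient who took no narcotic a BPI-30 non-responder. It applies only to patients with no analgesic at baseline, not to every newly started non-narcotic. Rule 2 can misclassify patients in either direction if known no-intake days are left out of the denominator, but that is an ambiguity and not an established error. Rule 3 lacks criteria and a stated time.

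The size cannot be estimated from the documents beyond the per-patient figures of 3.3 and 1.7 points. The range of 19.5 to 33 points around an assumed difference of 30 rests entirely on assumed rates and shows only that the direction is not fixed. The effect is confined to one supportive analysis with a nominal p-value. The primary endpoint, the testing hierarchy and the MMRM test of BPI Worst Pain are not affected.

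**What to change.** Revise the BPI-30 derivation in SAP 6.4.5 as follows.

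- **One term.** Use the same word in the criterion and all three rules. With the criterion as stated, only a newly started or increased narcotic counts. If all analgesics are meant, change the criterion itself. Say which rule covers an analgesic added to a continuing one.
- **Denominator.** Average intake over the 7-day window and state the length of the baseline window. Count days of known no intake as zero and keep days with missing records as missing. Do not set every day without a record to zero: that would turn missing data into an apparent fall in use and favour response. Retain the non-responder rule when endpoint data are not provided.
- **Drug switches.** Write down the criteria for the case-by-case review and complete it before treatment codes are released.

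The cost is SAP wording and programming on data already planned for collection. No protocol amendment and no additional patients are needed.
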